**Waiver of Consent/Authorization**

Indicate if you are requesting any of the following consent waivers  
Waiver of consent for use of records that include protected health information (a HIPAA waiver of Authorization)  
No  
Waiver or alteration of consent  
No  
Waiver of documentation of consent  
No  
Waiver of parental consent  
No

**Consent Procedures**

Is eligibility screening for this study conducted under a different IRB protocol?  
Yes  
Indicate NYSPI IRB #  
6582R  
Describe Study Consent Procedures  
Potential participants will sign the general screening (#6582R) consent form prior to initiating the screening

process. Following review of screening informed consent, an evaluation team consisting of a Masters- or Doctoral-level research psychologist and psychiatrist meets with potential participants. The baseline evaluation includes a full battery of self-report measures, a structured psychiatric evaluation (MINI interview), Hamilton depression scale, a physical examination, and laboratory assessments. Medical screening and laboratory work, include vital signs, a physical examination, ECG, serum chemistry, liver function tests, complete blood count, and urinalysis obtained by study personnel at STARS. Pregnancy tests will be conducted for women.

Indicate which of the following are employed as a part of screening or main study consent procedures

✓ Consent Form

### Study Procedures

Describe the procedures required for this study

Potential subjects will undergo a screening visit which will include a demographics questionnaire, medical history, physical examination, psychiatric evaluation, laboratory testing, and electrocardiogram. The MINI International Neuropsychiatric Interview (MINI) will be conducted to determine current DSM-5 diagnoses. Eligible participants will be offered the opportunity to participate in the research treatment study and informed consent using the IRB-approved consent form will be obtained by the research psychiatrist.

This is a 2-arm, randomized, placebo-controlled trial to obtain initial data regarding **feasibility and tolerability** of lorcaserin for increasing successful initiation onto XR-naltrexone. Sixty volunteers will be offered outpatient detoxification followed by a treatment with XR-naltrexone. Participants will be offered two injections of XR-naltrexone and weekly therapy. We selected adherence with naltrexone injections as the primary outcome because it is the most clinically meaningful outcome of this treatment.

The study will be entirely outpatient. Upon study entry, participants will begin clinic visits at the Substance Treatment and Research Service (STARS) clinic. All participants will visit the clinic twice weekly to

provide urine toxicology, report on adverse events, and complete additional assessments (Table 1), All participants will also receive medical management, a medication adherence focused psychosocial intervention that facilitates compliance with study medication and other study procedures, and promotes abstinence from opioids and other substances.

**Detoxification and Induction onto Injectable Naltrexone:** The detoxification-naltrexone induction will be performed at the STARS outpatient research clinic, which is outfitted with a detoxification suite. Participants come to the clinic daily visits to the clinic for safety, clinical monitoring and management of withdrawal. On Study Day -1, following the consent procedure, participants will be sent home with ancillary medications (clonidine, clonazepam, zolpidem) and will be instructed to abstain from opioids for 12-24 hours prior to Study Day 1 and they may use ancillary medication if needed. Buprenorphine is initiated usually on Day 1 after an overnight abstinence, given first as a test 2 mg dose followed by additional 4 mg dose in the clinic and 2 mg dose to take at night if discernible withdrawal symptoms are present. Before the buprenorphine dose, participants will be assessed for the severity of withdrawal using COWS, and will require a COWS score of 6 or greater, prior to administration of buprenorphine. On Day 2 patients are started on clonidine, clonazepam and if needed prochlorperazine for nausea. At the end of each clinic visit patients are sent home with additional ancillary medications to manage residual symptoms (clonidine, clonazepam and zolpidem). On Day 3 oral naltrexone is started at very low 1 mg dose, with and additional 3 mg dose administered 3 hours later. On Day 4 12.5 mg is administered and the patient's response is monitored. On Day 5 the target 25 mg of oral naltrexone is given at which point it is safe to administer the injection of naltrexone. On Days 1-5 COWS/SOWS assessments will be completed prior to administration of daily medications, 60 minutes after administration of oral naltrexone, and at the end of the study visit. All participants will receive naltrexone injections (Vivitrol 380 mg i.m.) under open label condition.

Compliance will be supported by observed ingestion of powdered doses of naltrexone as suspension in water. If opioid use occurs in combination with missed doses, a naloxone challenge will be administered to confirm that oral naltrexone will be tolerated; if necessary, an additional day of adjuvant medication only will be given. In patients at risk for greater withdrawal symptoms (e.g. history of severe withdrawal, substantial methadone use or more severe dependence (> 6 bags per day), or a strong reaction to the first daily dose of naltrexone), the procedure may be slowed down by 1 or 2 days.

**Ancillary medications:** A standing order of these medications will be available to patients and will include clonidine for myalgias (MDD= 0.3mg), prochlorperazine for nausea (MDD= 30mg), clonazepam to reduce anxiety and dysphoria (MDD= 1.5mg), zolpidem for insomnia (MDD=10mg).

Participants will be provided take-home doses of ancillary medications in small doses and on a tapering schedule for two weeks (including the detoxification week) to alleviate any protracted opiate withdrawal. Additional doses will be offered as clinically determined for participants experiencing continued withdrawal symptoms.

**Study Medications Dosing:** Study medications (lorcaserin or placebo) will be administered under double-blind conditions. Starting with day 1 of the induction period and during the subsequent six weeks of outpatient treatment all participants will receive two oral capsules (lorcaserin or matched placebo) twice daily. During the induction the first daily dose of lorcaserin **or placebo** 10mg will be given on Day 1 in the clinic 1 hour after the first dose of 2mg buprenorphine has been administered and the evening dose will be

taken at home at night. On Days 2-5, locaserin **or placebo** 10mg will be administered approximately 30 minutes prior to oral naltrexone.

**Double Blind Treatment Period:** Participants will be seen in the clinic at twice per week during weeks 2-7. At each visit the patient completes research ratings and the nurse collects vital signs and BMI, inquires about side effects, and obtains a urine sample under observation (Table 1). At each visit to STARS the patient meets with the research assistant to complete research ratings, including self-report of withdrawal, mood, and drug use. Side effects are reviewed at least weekly during the visit with a psychiatrist who will adjust medication dose if necessary. All participants will receive manualized, weekly therapy that it is derived from counseling aspects of BNT, emphasizing relapse prevention and adherence to medication. (Rothenberg et al., 2002). Participants will receive a 1-week supply of **lorcaserin or placebo** at a time.

Compliance with Lorcaserin/placebo: Timeline Followback (TLFB) pill count interview and weekly incentive for medication bottle return will be used to both enhance and measure medication compliance. To emphasize adherence to study medication and enhance reliability of the TLFB pill count, a \$10 cash card incentive is provided for return of both medication bottles and unused medications (if not taken). Whether or not the patient ingested medication is not tied to compensation for bottle and pill return. The results of the TLFB pill count and medication bottle return are discussed with participants by the research psychiatrist to enhance adherence.

Extended Release (XR) Injectable Naltrexone: Use of opiates presents different concerns in the management of patients receiving XR-naltrexone maintenance. Failure mode with XR-naltrexone is similar that a patient misses a scheduled injection, resumes heroin, and becomes re-addicted. However, because of the long duration of action of XR-naltrexone (full blockade lasts up to **one month** after the last injection with a partial blockade for another week) a grace period of at least 7 days can be expected during which the injection can be rescheduled without risk of relapse. If the patient misses a scheduled injection and takes an opioid during at least two of the seven days following the date of the scheduled injection, relapse will be suspected, and the psychiatrist will perform a naloxone challenge, if appropriate, using 0.8 mg naloxone, administered intramuscularly. The patient is followed clinically and withdrawal symptoms are assessed over the next half-hour. If the challenge is negative, the administration of XR-naltrexone will be resumed. If positive, then XR-naltrexone risks of precipitating withdrawal, and the injection will be postponed. However, because there are blood levels and partial blockade beyond Week 5, vulnerability to relapse may be more gradual, and the instance of mild or equivocal reactions to naloxone challenge more common. In this instance, a second challenge within 24-48 hours will be attempted, and if tolerated, the next injections can be given. **A urine pregnancy test will be obtained for female participants prior to administration of XR-Naltrexone.**

Procedures for Missed Doses of Long-acting Naltrexone: Missing a scheduled Vivitrol injection is the most important threat to the success of XR-naltrexone maintenance. In the event of a patient missing a scheduled injection, the clinic staff will immediately attempt to contact the patient to re-establish commitment to the naltrexone treatment and reschedule the injection within a 48-hour period. If the patient cannot attend the treatment clinic within that two-day time-frame, or cannot be located, the treatment team will use previously obtained locator information in an effort to locate the patient through emergency contacts and get him/her in for a clinic visit. If opioid use occurs in

combination with a missed Vivitrol injection, a naloxone challenge will be administered to confirm that the next long-acting naltrexone injection will be safely tolerated.

**Evaluation of Depression :Participants who meet criteria for a mood disorder (MDD) of mild to moderate severity will be followed closely during detoxification and subsequently. Mood will be assessed both in therapy sessions and in weekly MD visits, with repeated Ham-D scales. If a patient demonstrates significant depressive symptoms which persist following detoxification, we will offer the participant the option of beginning an antidepressant If deemed clinically warranted.**

Managing controlled substances: Currently the study is run under the NYS Controlled Substance license # 0400081 held by the NYS OMH and the DEA Researcher Registration # PN0093461 held by the NYSPI Pharmacy Department. [name] has obtained his own NYS Controlled Substance license and applied for a federal DEA research license. When he will obtain DEA Researcher Registration # the projects will be run under both his research specific NYS license, his DEA Researcher Registration and the NYS/OMH license and NYSPI DEA Researcher Registration. The drug stock of controlled substances for each project will be ordered, maintained and prepared under the Institutional registration at the NYSPI Pharmacy (OMH/NYS Controlled Substance license # 0400081). Packaged drugs (kits) will be transferred to the Principal Investigator ([name]) using a DEA 222 form with the address where the study will take place (e.g. [name]). Drugs or kits for individual patients will be transferred from the Institutional registration (#0400081) to the investigator registration using DEA 222 forms and transported by [name], FNP (supervisor of controlled substance activity) to the [name] research site. Drug will then be kept in the wall mounted, double-door, double locked storage cabinets at [name] until it is given to the participant.

You can upload charts or diagrams if any  
Naltrexone Lorca Study Process Image-4.24.17.pdf

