### Inclusion/Exclusion Criteria

Name the subject group/sub sample

All participants

Create or insert table to describe the inclusion criteria and methods to ascertain them

1. Individuals between the ages of 18-60  
(Clinical interview)

2. Meets DSM-5 criteria of current opioid use disorder present for at least six months, supported by a positive urine for **opioids**

---

( MINI interview by therapist, Clinical interview with psychiatrist, DSM-5 criteria review, and urine toxicology)

3. Seeking treatment for opioid use disorder

( Participant self-report, MINI interview by therapist, Clinical interview by psychiatrist)

4. Capable of giving informed consent and complying with study procedures

( Clinical interview by psychiatrist)

5. Not underweight; defined as  $BMI \geq 18.5$

( Calculation of BMI using weight and height of participant)

Create or insert table to describe the exclusion criteria and methods to ascertain them

1. Lifetime history of DSM-5 diagnosis of schizophrenia, schizoaffective disorder, or bipolar disorder

(MINI interview by therapist, Clinical interview by psychiatrist)

2. Current DSM-5 criteria for any other psychiatric disorder that in the investigator's judgment is unstable, would be disrupted by the study medication, or is likely to require pharmacotherapy or psychotherapy during the study period. Concurrent treatment with other psychotropic medication is exclusionary.

( MINI interview by therapist, Clinical interview and mental status exam by psychiatrist, contact with collateral information as needed and available)

3. Individuals who meet DSM-5 criteria for any substance use disorders - severe, other than opioid and nicotine use disorder. Physiological dependence on alcohol or sedative-hypnotics is exclusionary.

(MINI interview by therapist, Clinical interview by psychiatrist)

4. A recent history of binge-use of alcohol or sedative-hypnotics (using large amounts in a short time to severe intoxication or blackouts).

(Clinical interview by psychiatrist)

5. Pregnancy, lactation, or failure to use adequate contraceptive method in female patients who are currently engaging in sexual activity with men.

( Clinical interview by psychiatrist, physical examination and medical history by psychiatrist or NP, urine pregnancy test, serum HCG)

6. Unstable medical conditions, such as AIDS, cancer, uncontrolled hypertension (blood pressure  $> 140/90$ ), uncontrolled diabetes, pulmonary hypertension or heart disease.

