### Study Discontinuation

Drop out criteria during the screening and study period include:

- 1) Development of serious psychiatric symptoms as indicated by the Clinical Global Impression (CGI) improvement score of 6 (much worse than baseline) or greater for 2 consecutive weeks.
- 2) If the participant's continued opioid use places him/her at risk for self-destructive behavior or other harm as indicated by a CGI improvement score of 6 or more (much worse than baseline) for 2 consecutive weeks.
- 3) Development of serious medical condition(s) that may or may not be related to study participation (e.g., significant weight loss, serotonin syndrome) as assessed by weekly visits with the psychiatrist, vital sign measurements, weekly weight-ins, and monthly serum and urine laboratory studies
- 4) If the participant becomes pregnant as assessed by monthly urine pregnancy testing

- 5) Weight loss resulting in the participant becoming underweight (BMI<18.5). BMI will be calculated weekly.

Participants may be removed from the trial if they repeatedly miss scheduled appointments or clinical worsening necessitates more intensive treatment (drop out criteria are defined above). Subjects who develop serious psychiatric symptomatology (e.g., psychosis, suicidal ideation, severe depressive symptoms) during the study period will be dropped from the study and appropriate clinical referrals will be made. A patient who's continued opioid use, places them at risk for self-destructive behavior or otherwise places them at significant risk will be discontinued from the study. This would include, but not be limited to, patients who become unconscious after using, engage in destructive or violent behavior while intoxicated, report driving while intoxicated, or develop medical complications from their opioid use. In all cases where subjects are discontinued from the study, the clinical research staff will assume clinical responsibility for the subjects until clinical referrals are operational.

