### Potential Risks

**Study Medication Risks:** One of the main risks associated with participation is drug administration. Lorcaserin (or Belviq©) was approved by the FDA for treating obesity, is generally well tolerated, and has low abuse potential, though it is a schedule IV substance. The target daily dose of lorcaserin in the proposed study (20 mg) is the current FDA approved dose for the treatment of weight management. In clinical trials, headache was the only reported side effect to occur at a frequency much greater than placebo. Other possible side effects of lorcaserin include: constipation, dry mouth, headache, nausea, and dizziness. Some rare but serious side effects include hypoglycemia in patients with Type 2 diabetes, serotonin syndrome, agitation, confusion, hallucinations, arrhythmias, cardiac valve disease, depression, thoughts of suicide, and an erection lasting longer than 4 hours.

The combination of lorcaserin with other serotonergic medications (e.g., 5HT3 antagonist antiemetics, bupropion, triptans, SSRIs, SNRIs, TCAs, St. John's Wart, tryptophan), medications that impair the metabolism of serotonin (e.g., MAO inhibitors, dextromethorphan, tramadol, lithium), or antidopaminergic medications (e.g., antipsychotics) may enhance serotonergic effects, and this could result in rare but serious serotonin syndrome reaction. Signs of serotonin syndrome include: mental

status changes (e.g., anxiety, agitated delirium, restlessness, and disorientation); easy startle, autonomic manifestations (e.g., diaphoresis, tachycardia, hyperthermia, hypertension, vomiting, and diarrhea); and neuromuscular hyperactivity (e.g., tremor, muscle rigidity, myoclonus, hyperreflexia, and bilateral Babinski sign).

The combination of lorcaserin with ergot derivatives is contraindicated. The use of these drugs together may increase the risk of developing valvular heart disease in addition to enhancing serotonergic effects that may result in serotonin syndrome. The combination of lorcaserin with 5HT2B-R agonists (e.g., cabergoline) is contraindicated due to the increased risk of cardiac valvulopathy. Lorcaserin is a moderate CYP2D6 inhibitor and may decrease the clearance of drugs metabolized by CYP2D6, and thus raise these other drug levels increasing the risk of toxicity. Lorcaserin is contraindicated in pregnancy due to the fact that weight loss offers no clinical benefit in pregnancy and is advised against.

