### **2) Study Procedures**

Participants will be informed about the possible side effects and risks (listed above) of taking lorcaserin both alone and in combination with other medications through extensive discussions with staff psychiatrist during the consent process. Participants will be told to contact the clinic if they experience any adverse effects and given the number for the 24-hr physician on-call. All participants, both those not taking and taking concurrent medications, will be monitored closely throughout the study for possible signs and symptoms of serotonin syndrome and weight loss. Participants' mental status and physical health are monitored weekly during the study period by a psychiatrist. Vital signs will be obtained at each study visit. Weight will be assessed weekly to monitor for possible excessive weight loss and used to calculate BMI. At clinic visits, a physician will assess participants for signs and symptoms of adverse effects of lorcaserin, noting which if any symptoms are present, the severity of the symptoms, make adjustments to study medication dose, discontinue study medication, or withdraw the participant from the study if needed.

Female participants who are engaging in sexual activity with men must use adequate methods of contraception which will be discussed repeatedly during the screening process. Serum pregnancy tests will be conducted during screening and urine pregnancy tests will be performed monthly during the study. If a female participant does become pregnant or wishes to become pregnant, study medication will be immediately discontinued, she will be withdrawn from the study, and offered continuing nonpharmacological treatment (psychotherapy).

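### An antidepressant may be started while blinded capsules continue, although the protocol warns of serotonin syndrome with lorcaserin, and no step is required before the two overlap

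*Protocol*

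**What the plan says.** The depression paragraph in Protocol, Study Procedures, expects some depressed participants on study: "Participants who meet criteria for a mood disorder (MDD) of mild to moderate severity will be followed closely during detoxification and subsequently". Mood is assessed in therapy sessions and weekly physician visits, with repeated Ham-D ratings. If significant symptoms outlast detoxification, "we will offer the participant the option of beginning an antidepressant", subject to clinical judgement that it is warranted. No class is named or barred, and the capsules are not mentioned.

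Protocol, Potential Risks, lists drugs of concern alongside lorcaserin. As examples of serotonergic agents it gives "bupropion, triptans, SSRIs, SNRIs, TCAs" among others, and it names MAO inhibitors separately. Such combinations "may enhance serotonergic effects, and this could result in rare but serious serotonin syndrome reaction". The same section reserves the word contraindicated for ergot derivatives and 5HT2B agonists (and for pregnancy); it does not apply it to antidepressants.

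The sections disagree on how long capsules are taken. The Lay Summary has them stop after the second injection in week 5, Compensation refers to five weeks of study medication, and Study Medications Dosing gives the induction period plus six weeks. Under the SAP's Data analysis section, everyone except the research pharmacist is blind.

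**The concern.** A prescriber who follows the depression paragraph to the letter may add an SSRI, for example, to capsules that could be lorcaserin. The risk section names that combination as a possible cause of a serious reaction. The depression paragraph does not refer to the warning, and the prescriber cannot see the assignment. Two physicians with identical cases could reasonably act differently: one might stop the capsules, the other continue them. What is at stake is the safety of a small number of participants and consistent handling of study drug. No estimate or test in the SAP depends on it.

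**Working it through.** The plan states no figure on this point, so there is none to reproduce. The check has three parts.

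**1. Can the two drugs overlap?**

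- End of oral induction: Day 5, or Day 7 if the procedure is slowed by two days (Study Procedures, Detoxification and Induction).
- Last capsule: Day 35 (Lay Summary: end of week 1 plus four weeks, 7 + 28 = 35; Compensation agrees), Day 42 if the Lay Summary's five weeks follow the induction week, or Day 49 (Study Medications Dosing: one week plus six, 7 × 7 = 49).
- Possible overlap = last capsule day − end of induction.

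| Last capsule | Overlap from end of induction (days) | If symptoms must persist 7–14 days first (assumption) |
|---|---|---|
| Day 35 | 35 − 7 = 28 to 35 − 5 = 30 | 28 − 14 = 14 to 30 − 7 = 23 |
| Day 42 | 42 − 7 = 35 to 42 − 5 = 37 | 35 − 14 = 21 to 37 − 7 = 30 |
| Day 49 | 49 − 7 = 42 to 49 − 5 = 44 | 42 − 14 = 28 to 44 − 7 = 37 |

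Overlap is possible on every reading. These are not strict upper limits. The Lay Summary ties the last capsule to the second injection, which may be rescheduled.

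**2. Does another provision close the gap?**

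- Exclusion 2 bars concurrent psychotropic treatment and disorders "likely to require pharmacotherapy or psychotherapy during the study period". Exclusion 13 bars certain interacting drugs. Both act at entry, and the depression paragraph expressly provides for a later start.
- Under Double Blind Treatment Period, a psychiatrist reviews side effects at least weekly and can adjust the dose. This responds to side effects already present.
- Study Discontinuation removes participants with serious medical conditions ("e.g., significant weight loss, serotonin syndrome"), but only once they occur. It also removes those with serious psychiatric symptoms ("severe depressive symptoms) during the study period will be dropped from the study"), which leaves the mild to moderate cases.
- In the risk-minimisation part of the protocol, item 2 (Study Procedures) provides for discussion of combination risks at consent and for monitoring that includes people on concurrent medication. It also gives the physician power to "make adjustments to study medication dose, discontinue study medication, or withdraw the participant from the study if needed". That power is tied to adverse effects of lorcaserin, not to the start of an antidepressant.

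Each lowers the risk. None requires a decision about the capsules before co-administration.

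**3. How many starts would be on lorcaserin?**

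The documents give no rate of starts, so s is assumed. With 40 of 60 allocated to lorcaserin and equal start rates by arm, expected lorcaserin starts = s × 40/60, and P(at least one) = 1 − C(20, s)/C(60, s).

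| Starts s (assumed) | Expected on lorcaserin | P(at least one on lorcaserin) |
|---|---|---|
| 0 | 0 | 0 |
| 1 | 0.67 | 1 − 20/60 = 67% |
| 3 | 2 | 1 − 1,140/34,220 = 97% |
| 6 | 4 | over 99% |

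These percentages are chances that an assumed start falls in the lorcaserin arm. They are not risks of serotonin syndrome.

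**The case against.** The best defence is that the plan foresees this situation and leaves it to clinicians. The offer depends on clinical judgement, patients see a psychiatrist weekly, and capsules are supplied one week at a time. The risk section separates contraindicated combinations from those that only call for caution, and monitoring for serotonin syndrome explicitly covers people on other medication. A blinded prescriber can always act as if the participant were on lorcaserin. The reaction is described as rare, and starts may be few or none.

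Much of this stands. A reader might infer that the protocol authorises a contraindicated combination. It does not, because the antidepressant classes carry a warning only. A reader might also take the psychotropic exclusion as an on-study ban that the depression paragraph breaks. It is an entry criterion. The assignment figures are also soft: they treat all 60 randomised participants as available, although the protocol projects 40 completers, and equal start rates are uncertain because depression is itself listed as a rare serious effect of lorcaserin.

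The defence does not supply a required step. Discretion tied to adverse effects begins after the combination has begun, and assuming active drug is sensible practice that the protocol does not state.

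**Conclusion.** The point holds as a gap between the depression paragraph and the risk section. The plan permits a combination it warns about, for roughly 4 to 6 weeks from the end of detoxification, and requires nothing beforehand. The overlap rests on the protocol's own dates. The shorter figures rest on an assumed 7 to 14 days of persisting symptoms, and the assignment figures on assumed start counts.

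A reader might go further and infer a quantified harm or a threat to the trial's findings. The documents support neither: they give no rate of starts or of reactions, and nothing here biases a planned analysis. The size of the safety benefit therefore cannot be stated. This is a cheap safety improvement that should be made.

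**What to change.** Add to the depression paragraph:

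- The prescriber assumes that every participant is taking lorcaserin.
- Before any antidepressant with serotonergic action, any MAO inhibitor, or bupropion is started, blinded capsules are stopped without unblinding and unused capsules are collected. The rule is worded by action because the risk section's list gives examples only.
- One interval between the last capsule and the first antidepressant dose is written into the protocol in advance, taken from the lorcaserin labelling, and applies to both arms. The research pharmacist, who works with the randomization sequence, then has no part in decisions about individual participants.

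State in Study Discontinuation that this stops study drug only. XR-naltrexone, visits and intent-to-treat follow-up continue. Record the stop on the weekly Concomitant Medications Form; the existing bottle-return procedure can handle collection.

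**Cost.** A short paragraph and one clarifying line, with no added patients, visits or forms. The mild to moderate participants affected lose their remaining capsules and wait out the interval before antidepressant treatment. Severe cases are already dropped and referred, so their care is not delayed.

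The second-injection comparison, primary in the protocol and secondary in the SAP, would be slightly diluted. If affected lorcaserin participants lost all benefit and the effect were otherwise uniform, the difference would shrink by 0.67/40 = 1.7%, 2/40 = 5% or 4/40 = 10% of its size for 1, 3 or 6 starts. With 3 starts, an assumed 20-point difference would become 20 × 0.95 = 19 points. The SAP's primary outcome, induction, is essentially settled by then.
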